1 STUDY DESIGN

This research will examine the initial feasibility and acceptability of a values-affirmation, education, and skills-training intervention targeting heart failure (HF) medication adherence using the NIH Stage Model for Behavioral Intervention Development (Onken et al., 2014).

Design: This study is a Stage 1B trial and will use a randomized controlled trial design. Participants will be randomized 1:1 basis to the Values-affirmation Intervention condition (n = 25) or Usual Care (n = 25).

Setting: Study assessments and intervention delivery will occur either at the participant's home or The Miriam Hospital's Center for Behavioral and Preventive Medicine (CBPM). The location will be determined by participant preference. Data management and analysis will be housed at CBPM.

Study Duration: Study duration is estimated to be 21-24 months from the time of enrollment of the first subject to completion of data collection. Individual participants will complete the protocol within 8-10 weeks from the time of the baseline visit until the end-of-treatment assessment. Study completion is defined as completion of the baseline and end-of-treatment assessments, intervention content, and medication monitoring period.

Sample: 50 older adults with HF, ages 50 and older, who are enrolled in a CR program in Providence, Rhode Island will be recruited. We aim to recruit a sample that is 51% women and 30% individuals who identify as a NIH-defined racial or ethnic minority.

2 PRIMARY OBJECTIVE

The primary objectives of this study are to assess randomized controlled trial feasibility and acceptability through a randomized controlled pilot trial. Primary endpoints are feasibility of study procedures (e.g., monthly recruitment rates, percent of enrolled participants who complete the study), and acceptability (e.g., self-reported patient acceptability questionnaire). We hypothesize that the study and intervention will be 1) feasible, and 2) acceptable.

3 SELECTION AND ENROLLMENT OF PARTICIPANTS

3.1 Inclusion Criteria

Older adults with a diagnosis of HF upon admission and other CR participants with a HF diagnosis regardless of CR referral reason will be eligible for inclusion (e.g., an individual referred for CR following a myocardial infarction who also has a HF diagnosis will be invited to participate).

Additional inclusion criteria will include: (1) adults \geq the age of 50 at the time of study initiation and (2) English-speaking.

3.2 Exclusion Criteria

(1) current participation in a medication-monitoring clinical or research protocol, (2) severe cognitive impairment on cognitive screening measures or diagnosis of Alzheimer's or dementia, (3) current suicidality, (4) acute psychosis, (5) chart documentation of NYHA-class IV HF, or

(6) patient report that someone other than the patient is primarily responsible for the patient's medication management and medication-taking.

3.3 Study Enrollment Procedures

Recruitment

Participants will be recruited from the Cardiac Rehabilitation Center at the Miriam Hospital (Providence, RI) and Lifespan Cardiovascular Institute, Lifespan Ambulatory Care Center (East Greenwich, RI). Patients deemed to meet initial inclusion criteria (i.e., HF diagnosis, aged ≥ 50 years, no chart documentation of severe cognitive impairment or dementia, English-speaking) based on chart review will either be approached in the clinic or will be mailed a letter invitation to participate and contacted via phone one week later. Individuals who are approached in clinic will be asked to complete a "Consent to Contact" form. If patients do not respond to two telephone calls, they will not be telephoned again.

Screening

Patients will be asked to complete eligibility screening via telephone. They will also be asked to complete the Blessed Orientation Memory Concentration test (BOMC) to screen for significant cognitive impairment. Participants who score 10 or greater on the BOMC will not be eligible.

4 ASSESSMENT PROCEDURES

4.1.1 Baseline Assessments (Visit 1)

- Demographics (self-reported) and medical comorbidity (supplemented via medical chart review).
- The Medication Management Instrument for Deficiencies in the Elderly will assess individual patient knowledge of their specific medication instructions.
- Timeline follow-back medication adherence interview. Participants will be prompted to recall missed or late medications for each day in backwards order during the preceding 7 days.
- Pill Count of 1 medication: We will conduct a pill count of ONE medication per patient using the criteria adopted by Wu et al.
- Medication Adherence Scale.
- LifeWindows Information--Motivation--Behavioral Skills ART Adherence Questionnaire was adapted for use in HF to assess HF medication knowledge, related motivation, and behavioral skills in line with the sIMB-CIM model.
- The Rapid Estimate of Adult Literacy in Medicine—Short Form will assess health literacy.
- Valued Living Questionnaire
- Free, cued, and delayed recall will be measured using the Memory Impairment Screen-Delayed.
- Patient Health Questionnaire 9
- Positive and Negative Affect Scale-Short Form
- Perceived Stress Scale-Short Form
- ENRICH'D Social Support questionnaire
- Patient-Reported Outcomes Measurement Information System (PROMIS) Self-Efficacy

for Managing Chronic Conditions- Managing Medications and Treatment- Short Form 4a

- the Minnesota Living with Heart Failure Questionnaire (MLHFQ)
- EuroQual-5 Dimension (EQ-5D)
- Monitored Medication Adherence

Participants will also be asked to use a MEMS cap pill bottle to monitor medications for approximately 8 weeks (from the baseline assessment through the end-of-treatment assessment). We will monitor ONE medication per patient using the criteria adopted by Wu et al. Briefly, if the patient takes any HF medication *twice* a day, this medication will be MEMS-monitored. If all HF medications have the same daily prescription schedule, the β -blocker will be monitored. If the patient does not receive a β -blocker, the ACE inhibitor or the angiotensin receptor blocker will be used instead. If none of these drugs is prescribed, the aldosterone antagonist or statin, or digoxin or diuretic will be monitored. Participants will receive a MEMS bottle at the baseline visit and will be instructed to open it only when they actually take their medication; they will also be trained to keep track of unscheduled lid openings (i.e. refills, accidental openings) in a diary; these events will be removed prior to analysis. After the baseline visit, participants will enter a 30-day run-in for the assessment of baseline adherence. Participants will start using the cap on the day following the baseline visit (=time 0), and the intervention will start 30 days later; this 30-day period will be considered our baseline.

MEMS Caps are designed to be easily opened and closed, and to be very similar in design to pill bottles commonly used commercially. Participants will be asked to review their medication regimen with PI/SRA. Participants will be asked to fill the bottle with their prescribed heart medication selected for monitoring. Prior to use, a study team member will demonstrate appropriate use of the pill bottle and will invite participants to practice opening and closing the containers.

Written instructions will be provided to all participants, including study staff contact information. Participants will be encouraged to contact staff in the event of any questions or concerns. One week following the baseline assessment and initiation of monitoring, study staff will call the participant to ask if there are any questions regarding use of the devices. Any emergent questions will be answered.

4.1.2 Intervention Session + Pill Count Check OR Pill Count Check only (Visit 2)

- Following completion of the Baseline monitoring period, study staff will contact the participant and inform the participant of their randomization assignment via telephone, and schedule Visit 2. Visit 2 will be conducted either at the participant's home or the study office, as determined by participant preference. Individuals assigned to the Intervention condition will also complete the intervention at this session (see details in Section 6). For participants in both conditions, we will again conduct a pill count of ONE medication per patient using the criteria adopted by Wu et al. described above.

4.1.3 Final Evaluation (Visit 3)

- 7-day Timeline follow-back procedure to assess self-reported medication adherence.
- Medication Adherence Scale

- Pill Count of 1 medication
- Valued Living Questionnaire
- Patient Health Questionnaire 9
- Positive and Negative Affect Scale- Short Form
- Perceived Stress Scale- Short Form.
- ENRICHD Social Support questionnaire
- Patient-Reported Outcomes Measurement Information System: Patient-Reported Outcomes Measurement Information System (PROMIS) Self-Efficacy for Managing Chronic Conditions- Managing Medications and Treatment- Short Form 4a
- Minnesota Living with Heart Failure Questionnaire (MLHFQ)
- EuroQual-5 Dimension (EQ-5D)
- Study and Treatment Acceptability. Participants will complete a self-report measure which gathers feedback about the study.

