4.2 Interventions, Administration, and Duration

Following completion of the baseline adherence monitoring period, participants will be randomly assigned to one of two conditions. Participants will be scheduled for Visit 2 at the end of the baseline adherence monitoring period. Participants will be randomized and notified of group assignment upon arrival to Visit 2.

Group A (Usual Care): Participants assigned to Group A will receive the standard care that they would receive as part of cardiac rehabilitation.

Group B (Values affirmation intervention condition): Participants assigned to Group B will receive standard care in addition to the Values affirmation intervention condition. Participants will complete a one intervention session with the study interventionist (about 60 minutes). The session will include:

1. Participation in a values-affirmation exercise (i.e., Values card sort activity).
2. Working with the interventionist to devise a way to tangibly connect that value with medication-taking (i.e., placing a label with a word or picture of the value on a pill bottle or display next to the pill bottle). Values labels will be based on images presented on the values card sort cards or personalized pictures taken with a Lifespan-issued tablet and printed on site with a portable photo printer. Once the picture is printed it will be deleted from the tablet.
3. Provision and review of a patient education workbook that recommendations for skills training activities to improve regimen management.

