6 PRIMARY ENDPOINTS

Primary Endpoints:

- 1) Recruitment feasibility will be determined through examination of the percentage of eligible patients who enroll in the study.
- 2) Study feasibility will be calculated as the percentage of individuals who were enrolled and completed both the baseline assessment, intervention (when applicable), monitoring period, and end-of-treatment assessment. Feasibility of procedures will be defined as achieving a retention rate of 80%.
- 3) Patient acceptance of the intervention will be determined by mean satisfaction ratings rated on self-report measures with Likert-type questions and assessed through open-ended responding. Adequate acceptability will be defined as $\geq 80\%$ endorsement of being at least somewhat satisfied with participation.

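### Acceptability is rated only at Visit 3, so treated participants who do not return give no rating; at 80% retention, a pass is compatible with 64% to 84% of those treated being satisfied

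*Protocol*

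**What the plan says.** Protocol 4.2 describes the contact with the interventionist: "Participants will complete a one intervention session with the study interventionist (about 60 minutes"). Protocol 4.1.2 places it at Visit 2. The only measurement listed for that visit is a pill count: "For participants in both conditions, we will again conduct a pill count of ONE medication per patient".

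The acceptability form appears once, among the final assessments in Protocol 4.1.3: "Participants will complete a self-report measure which gathers feedback about the study". Neither document describes a rating after the session or at withdrawal.

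Protocol 6 item 3 makes this a primary endpoint: "Patient acceptance of the intervention will be determined by mean satisfaction ratings rated on self-report measures". The pass mark is at least 80% "endorsement of being at least somewhat satisfied with participation". SAP item 3 under the primary endpoints repeats it. Neither document says which arm or denominator the 80% refers to, or how a missing rating is counted. Protocol 6 item 2 and SAP item 2 set the retention mark at 80%, so a loss of one participant in five is acceptable under the plan.

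**The concern.** The endpoint is meant to show whether patients accept the intervention, and dissatisfaction with the session is a plausible reason for not coming back. With one rating point, at the last visit, acceptability is observed only in those who were retained. Two primary endpoints are then linked: losses that lower retention may also remove unfavourable ratings from the acceptability percentage. Ratings that were never taken cannot be recovered at analysis. A larger trial could be planned on a pass that describes the returners and not everyone who had the session.

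**Working it through.** The documents derive no sample size or error rate for this endpoint, so there is no stated figure to reproduce. The 80% mark is a fixed descriptive threshold.

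**Inputs from the documents**
- Arm size: 25 intervention, 25 usual care (Protocol 1).
- Session: "the intervention will start 30 days later", counted from the start of cap use (Protocol 4.1.1).
- Final visit: participants monitor "medications for approximately 8 weeks (from the baseline assessment through the end-of-treatment assessment") (Protocol 4.1.1); Protocol 1 gives 8 to 10 weeks.
- Retention mark 80%; acceptability mark 80% (Protocol 6).

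**Step 1: gap between session and rating**
- At 8 weeks: 56 − 30 = 26 days.
- At 10 weeks: 70 − 30 = 40 days.

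This is about 4 to 6 weeks. Cap use starts the day after baseline, which takes off one day. A Visit 2 held later than day 30 shortens the gap further.

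**Step 2: what a pass says about everyone treated**

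Assume that all 25 intervention participants have the session and that all losses come after it. With n raters and s satisfied raters, satisfaction among the 25 lies between s/25 (no non-rater satisfied) and (s + 25 − n)/25 (all non-raters satisfied).

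| Retention | Raters n | Fewest satisfied to pass | Among raters | Range among all 25 |
|---|---|---|---|---|
| 100% | 25 | 20 | 80% | 80% |
| 90% | 23 | 19 | 82.6% | 76% to 84% |
| 80% | 20 | 16 | 80% | 64% (16/25) to 84% (21/25) |

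If both arms rate, 32 of 40 raters gives the same range over 50: 32/50 = 64% to 42/50 = 84%.

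**Step 3: direction of any bias**

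Let p be true satisfaction, and dS and dD the dropout rates in satisfied and dissatisfied participants. The documents give none of these, so all values here are assumptions. Then

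expected observed rate = p(1 − dS) / [p(1 − dS) + (1 − p)(1 − dD)].

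| p | dS | dD | Calculation | Observed | Retention |
|---|---|---|---|---|---|
| 75% | 20% | 20% | 0.600/0.800 | 75.0% | 80% |
| 75% | 10% | 30% | 0.675/0.850 | 79.4% | 85% |
| 75% | 10% | 50% | 0.675/0.800 | 84.4% | 80% |
| 75% | 30% | 10% | 0.525/0.750 | 70.0% | 75% |
| 70% | 10% | 30% | 0.630/0.840 | 75.0% | 84% |
| 70% | 8% | 50% | 0.644/0.794 | 81.1% | 79% |

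Equal dropout gives no bias, and the reverse pattern biases downward. Upward bias grows with the excess of dD over dS.

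**Step 4: effect on the chance of a pass**

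Take p = 75% and 20 raters. The binomial chance of at least 16 satisfied is 0.42 with equal dropout and 0.81 with 10% against 50%. With all 25 rating, the chance of at least 20 satisfied is 0.38.

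**The case against.** A reader might infer that the 80% mark is biased upward and that people put off by the session never rate it. The documents do not support either statement. Upward bias needs dissatisfied participants to leave more often, and no dropout figure by satisfaction is given. Dissatisfied participants who return do rate. Return is also encouraged: $60 of the $90 is paid after Visit 3, and home visits are offered. A true 70% reads as a pass under 8% against 50% dropout, but under 10% against 30% it reads as 75% and still fails. All of this stands.

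Selective dropout is not wholly hidden, because it also counts against retention. That stands in part. The retention mark is pooled over arms, and the 75% case with 10% against 50% dropout sits exactly at 80% retention. A retention figure does not show why people left.

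The SAP says all randomized participants are included in analyses, and it compares completers with non-completers. The first cannot supply a rating that was never taken, and no rule for missing ratings is given. The second concerns baseline characteristics, not satisfaction. Counting non-raters as not satisfied would remove the upward bias, but neither document says so. At 80% retention that rule reaches 80% only if all 20 raters are satisfied (20/25).

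A reader might also infer that the 80% mark should move to Visit 2. The documents do not support this. The criterion is satisfaction with participation, which includes monitoring and assessments, and the value label and workbook are evidently for use after the session. An end-of-treatment rating is defensible, and a rating minutes after a one-to-one session may be polite. This objection stands, so the remedy is an added rating and not a relocated one.

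**Conclusion.** The point holds as a gap in data collection with a possible, not a demonstrated, bias. A primary endpoint is rated only about 4 to 6 weeks after the session, and treated participants who do not return contribute no rating. If they are less satisfied than returners, the percentage is too high; if they are more satisfied, it is too low. The plan collects nothing that would tell these apart.

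The size that rests on the fewest assumptions is the range at the plan's own retention mark: 80% among raters is compatible with 64% to 84% of those treated. It assumes that 80% retention applies within the intervention arm and that every loss follows the session; losses during the run-in would narrow it. The dropout scenarios show only how direction depends on who leaves. The change is worth making because the endpoint is primary, the missing ratings cannot be obtained later, and the cost is small.

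**What to change.** - **Protocol 4.1.2:** add a short satisfaction form that intervention-arm participants complete privately at the end of Visit 2, for example returned in a sealed envelope.
- **Protocol 4.1.3:** no change. The Visit 3 measure stays the basis of the 80% mark.
- **Protocol 6 item 3 and SAP item 3:** state that, in a sensitivity analysis of the 80% mark, the Visit 2 rating is used for treated participants with no Visit 3 rating. Report it beside the result with non-raters counted as not satisfied.

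In the example above, with 16 of 20 satisfied at Visit 3 and five non-returners, the sensitivity analysis reaches 80% if at least four of the five were satisfied at Visit 2: (16 + 4)/25 = 80%. The companion figure is 16/25 = 64%.

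The cost is a one-page form, a few minutes at an existing visit, and one sentence in each of the three places. Ratings given just after the session may be somewhat polite, which is why they supplement the Visit 3 rating and do not replace it.

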4.2 Interventions, Administration, and Duration

Following completion of the baseline adherence monitoring period, participants will be randomly assigned to one of two conditions. Participants will be scheduled for Visit 2 at the end of the baseline adherence monitoring period. Participants will be randomized and notified of group assignment upon arrival to Visit 2.

Group A (Usual Care): Participants assigned to Group A will receive the standard care that they would receive as part of cardiac rehabilitation.

Group B (Values affirmation intervention condition): Participants assigned to Group B will receive standard care in addition to the Values affirmation intervention condition. Participants will complete a one intervention session with the study interventionist (about 60 minutes). The session will include:

1. Participation in a values-affirmation exercise (i.e., Values card sort activity).
2. Working with the interventionist to devise a way to tangibly connect that value with medication-taking (i.e., placing a label with a word or picture of the value on a pill bottle or display next to the pill bottle). Values labels will be based on images presented on the values card sort cards or personalized pictures taken with a Lifespan-issued tablet and printed on site with a portable photo printer. Once the picture is printed it will be deleted from the tablet.
3. Provision and review of a patient education workbook that recommendations for skills training activities to improve regimen management.

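### Protocol 4.1.2 discloses the arm by telephone before Visit 2, while 4.2 randomises and discloses on arrival at Visit 2, so it is open whether someone who misses Visit 2 was randomised

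*Protocol*

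**What the plan says.** Two protocol sections describe the same step differently.

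- Section 4.1.2: after the baseline monitoring period, staff contact the participant and "inform the participant of their randomization assignment via telephone, and schedule Visit 2".
- Section 4.2: "Participants will be randomized and notified of group assignment upon arrival to Visit 2".

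The other statements on allocation do not choose between them. Section 4.2 opens with "Following completion of the baseline adherence monitoring period, participants will be randomly assigned to one of two conditions", which fits either version. Section 1 gives the ratio ("Participants will be randomized 1:1 basis to the Values-affirmation Intervention condition") and 25 per arm, but no time. The SAP gives no time of randomisation.

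Three further provisions matter.

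- The SAP's General Approach defines intent-to-treat as the inclusion of everyone randomised.
- Visit 2 differs by arm. The heading of 4.1.2 offers either the session with a pill count or the pill count alone, and the text adds "For participants in both conditions, we will again conduct a pill count of ONE medication per patient".
- Section 5 pays $30 after Visit 1 and $60 after Visit 3. For Visit 2 there is no cash, only a parking voucher for those who attend at the study building.

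On a separate matter, the SAP runs every secondary analysis both with and without adjustment for covariates and the baseline score. It does not list the covariates or say which version leads.

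**The concern.** The moment of randomisation decides who is in a set defined as everyone randomised. Here that moment falls either before or at a visit that some people may miss.

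The two versions also differ in what a participant knows when deciding whether to come. If the arm is disclosed by telephone, one person is choosing whether to attend a session of about 60 minutes and another whether to attend for a pill count only. Attendance can then differ by arm, in a direction that the documents do not allow one to predict. If the arm is disclosed on arrival, attendance at Visit 2 cannot depend on it.

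This is a pilot meant to show that randomised procedures are feasible, so the point of allocation is one of the procedures under test.

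**Working it through.** **Can both sections be followed?** An assignment disclosed in the call that books Visit 2 exists before Visit 2. Section 4.2 creates it at Visit 2. For one participant these exclude each other. Section 4.2 also has a sentence on booking Visit 2, but it can be read either way and I do not rely on it.

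**Who changes status?** Someone who finishes the run-in and does not attend Visit 2 is randomised under 4.1.2 and not randomised under 4.2. The documents give no rate of missing Visit 2, so I assume a range. With 50 people finishing the run-in:

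- 5%: 50 × 0.05 = 2.5, that is 2 or 3 people
- 10%: 50 × 0.10 = 5 people
- 20%: 50 × 0.20 = 10 people

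**Effect on a between-group estimate.** A person with no Visit 3 outcome does not change an ANCOVA estimate, whichever set holds them. The sets give different estimates only through people who miss Visit 2 but attend Visit 3. Let p be the share missing Visit 2 (the same in both arms) and q the share of those who attend Visit 3. Suppose that they gain nothing from a session they did not receive. Their share of the intervention arm's Visit 3 outcomes, which is also the proportional shrinkage of the estimate under 4.1.2 relative to 4.2, is pq / (1 − p + pq).

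| p | q = 0 | q = 0.5 | q = 1 |
|---|---|---|---|
| 0.05 | 0% | 0.025/0.975 = 3% | 5% |
| 0.10 | 0% | 0.05/0.95 = 5% | 10% |
| 0.20 | 0% | 0.10/0.90 = 11% | 20% |

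**Effect on the primary endpoints.** The denominators (eligible patients for recruitment, enrolled participants for retention) do not depend on when people are randomised. The numerator of the protocol's study-feasibility endpoint (Section 6, item 2) can, because it requires completion of the intervention where that applies. Take someone who misses Visit 2 but completes monitoring and Visit 3. Under 4.1.2, if allocated to the intervention, that person is a non-completer. Under 4.2 no arm was ever assigned, so the intervention arguably does not apply and the person may count as complete. With 50 enrolled, each such person moves the result by 1/50 = 2 percentage points, against a target of 80%. The SAP's retention definition leaves the intervention out, so on that definition the question does not arise.

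**The separate point on adjustment.** Assume 26% and 10% of outcomes are lost in the two arms, leaving 25 × 0.74 = 18.5 and 25 × 0.90 = 22.5. The unadjusted standard error is √(1/18.5 + 1/22.5) = 0.31 SD. Baseline adjustment multiplies it by about √(1 − r²). For an assumed correlation r = 0.6 this is 0.31 × 0.80 = 0.25 SD, and for r = 0.4 it is 0.31 × 0.92 = 0.29 SD. In 40,000 simulated trials with 25 per arm, no true effect and r from 0.3 to 0.7, at least one of the two versions gave p < .05 in 6.3% to 8.1% of trials. The two versions disagreed on significance in 2.6% to 6.4%.

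**The case against.** The strongest reply is that the SAP does define its analysis set. Whichever procedure is run, the allocation record will show who was randomised. That is correct: a reader might infer that the trial has no analysis set, and the documents do not support that. What is open is the procedure, and with it whether those who miss Visit 2 belong to the set.

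It can also be said that few people may miss Visit 2, since it can take place at home, and that Visit 3 is paid. This stands as a limit on size. The documents give no rate, and the effect on an estimate is nil if those who miss Visit 2 also miss Visit 3.

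A reader might go further and infer that telephone disclosure biases the treatment comparison by some definite amount. One can produce such figures by assuming that loss at Visit 3 differs by arm and depends on baseline or outcome. They would not measure this defect. Participants know their arm from Visit 2 onward under either version, so loss after that point can differ by arm either way, and nothing in the documents links missing Visit 2 to missing Visit 3.

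On adjustment, reporting both versions is common in a pilot with descriptive primary endpoints, and naming ANCOVA already suggests a covariate. This makes the point minor, but it still leaves two unranked results per endpoint.

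**Conclusion.** The contradiction is certain on the text and should be corrected. Its consequence is modest and cannot be sized from the documents. On the assumed 5% to 20% missing Visit 2, between 2 or 3 and 10 of 50 people change status, and the intervention estimate differs by 0% to 20% of its value depending on how many of them attend Visit 3.

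The effect falls mainly on secondary and exploratory comparisons. Because the primary denominators are fixed, a reader might conclude that the primary endpoints are untouched. That is not quite so for the protocol's study-feasibility endpoint, whose numerator includes the intervention where applicable.

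The lack of a lead secondary analysis is a separate, minor matter. Its case is precision and a single lead result per endpoint, and the gain depends on the assumed correlations.

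**What to change.** 1. Amend Protocol 4.1.2 so that the call only schedules Visit 2. Keep the 4.2 rule that randomisation and disclosure take place at Visit 2. This is the better choice because attendance at Visit 2 then cannot depend on the arm.
2. State in the SAP that the intent-to-treat set counts people as randomised from that point.
3. As an added recommendation, do the Visit 2 pill count before disclosure. Section 4.2 does not say this, and 4.1.2 mentions the count without placing it in order.
4. If the telephone version is kept instead, count everyone as randomised from the call and report non-attendance at Visit 2 by arm.
5. Separately, name the baseline-adjusted ANCOVA in the SAP as the lead analysis for each secondary endpoint that has a baseline score, list the covariates, and keep the unadjusted version as a sensitivity analysis.

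All of this is wording and needs no new data. The cost of the on-arrival rule is that a session must be ready at every Visit 2, including home visits. The documents do not say who staffs these visits. If the interventionist attends anyway, the extra time is close to nil. Otherwise it is at most about 25 usual-care visits × 60 minutes = 25 hours held in reserve, plus travel.
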